Once hemostasis has been achieved, CPB will be initiated (if low flow CPB had not been continued throughout) for reperfusion and slow rewarming. The goal will be to keep the total time of circulatory arrest under 1 hour and to minimize the duration of low flow at profound hypothermia. The rewarming rate will be targeted at 0.5°C/min. During rewarming, transfusions of standard (i.e., for clinical use) packed red blood cells, fresh frozen plasma, cryoprecipitate, and platelets will be administered to achieve a hemoglobin of at least 8 gm/dl, normalized prothrombin time (INR <1.5) and activated partial thromboplastin time (PTT), fibrinogen level of 150 mg/dl, and platelet count of >100,000. Thromboelastograms may also be followed. Activated clotting times (ACT) will be monitored. If hemostasis is acceptable, the ACT will be maintained at >180 sec with intravenous heparin as needed until CPB is discontinued.

Rewarming will continue until Tty reaches 34°C. Mild hypothermia (Tty 34°C) may be maintained for 12 h to optimize neurologic recovery using external cooling plus sedation and paralysis as needed. If coagulopathy persists despite aggressive correction with blood products (to platelet count of 100,000 and normal PT/PTT and fibrinogen), rewarming to normothermia may be considered. More prolonged post-resuscitation hypothermia may be considered in selected subjects with poor neurologic function at 12 hours with no contraindication to mild hypothermia.

Shivering will be treated with sedation (propofol), analgesia (fentanyl), and, if necessary, neuromuscular blockade.

Decannulation should be performed as soon as the subject has sufficiently stable spontaneous circulation to be weaned from CPB. The thoracotomy should then be closed. If the subject requires more prolonged circulatory support, the use of Extracorporeal Life Support (ECLS) via extrathoracic (usually femoral or jugular) cannulation can be considered. ECLS may be appropriate for a subject who can not be weaned from CPB because of hypotension (despite inotropes/vasopressors or an intra-aortic balloon pump) or inadequate oxygenation (e.g., PaO2 to FiO2 ratio consistently less than 100), yet otherwise seems to have potential for long-term survival.

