The experimental aspects of this protocol that are different from the standard of care for trauma patients include the rapid cooling with the saline flush, reperfusion/rewarming using CPB, post-resuscitation mild hypothermia, and the potential for long-term ECLS. Standard operative management of injuries will occur simultaneously with these components. The experimental treatment will be completed when the subject has been rewarmed to normothermia and is not on ECLS.

Failure of EPR:

Technical issues may lead to inability to initiate adequate cooling for EPR. These issues could include (but are not limited to): inability to place the cannulae (most likely because of the subject's anatomy or specific injury pattern), displacement of cannulae after placement, and inability to establish adequate flow and thus adequate cooling. Minimal cooling rates are defined as achieving Tty 30°C within 15 min, 20°C within 30 min, and 10°C within 60 min. Failure of the pump is also a possibility, although this is unlikely as these devices are used routinely for CPB in the operating room. If EPR cannot technically be adequately induced, the investigator may elect to discontinue resuscitative efforts.

Personnel:

The trauma surgeon and the trauma team will perform the resuscitation. They will place the cannulae and initiate EPR. If possible, a perfusionist may assist with pumping for the cold fluid and with CPB. The cooperation of cardiac surgeons will be needed. A part-time coordinator will be involved in training, stocking the equipment needed for EPR, and collecting data. In addition, the coordinator may participate in EPR induction.

Because this is the first trial of EPR, subjects will not be enrolled when the trained team is not available.

Equipment for EPR:

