Title 10 United States Code 980 states that "Funds appropriated to the Department of Defense may not be used for research involving a human being as an experimental subject unless- (1) the informed consent of the subject is obtained in advance; or (2) in the case of research intended to be beneficial to the subject, the informed consent may be obtained from a legal representative of the subject."

Even though there is intent to benefit patients enrolled in this study, the informed consent of the LAR is likely not going to be possible to secure in advanced, hence a waiver of 10 USC 980 will be requested.

XI. DATA COLLECTION, ANALYSIS and COORDINATION

Data collection

Procedures to assess efficacy:

The primary outcome variable will be survival to hospital discharge without major disability (Glasgow Outcome Scale-Extended >5) after resuscitation with EPR in exsanguinating trauma patients, compared to concurrent or historic control patients. the ability (feasibility) and safety of inducing EPR. Secondary outcomes will include: 1) the feasibility and safety of rapidly inducing profound cerebral hypothermia for EPR in exsanguinating trauma patients, 2) 28-day survival, 3) 6 and 12-month neurologic functional outcome (Glasgow Outcome Score Extended [GOSE]) and SF-36, and 4) the development of multiple organ dysfunction syndrome (MODS) (see Table: Multiple Organ Dysfunction Score) in the EPR group, as compared to a concurrent control group and historical controls.

Once the EPR subject has been rewarmed and, if possible, weaned from CPB, there will be no additional invasive procedures performed on the subject for the specific purpose of the research study. The subject will continue to undergo standard medical procedures as indicated for the clinical care of his/her trauma injury.

For subjects in both arms of the study, the medical record will be utilized to determine the occurrence of multiple organ system dysfunction or death.

The MODS Score (Table) will be utilized to quantify the level of organ system dysfunction.

Neurologic functional outcome will be assessed in survivors using the GOSE and SF-36 at 6 and 12 months. If the subject is discharged from the hospital prior to either of these dates, GOSE information will be obtain via telephone calls to the subject or the subject's LAR.

			Score		
Organ system	0	1	2	3	4
Respiratory (PO ₂ /FiO ₂)	>300	226-300	151-225	76-150	< 75

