Renal (serum creatinine - µmol/l)	< 1.1	1.2-2.3	2.4-3.9	4.0-5.6	>5.7
Hepatic (serum bilirubin - µmol/l)	< 1.1	1.2-3.5	3.6-7.1	7.2-14.1	>14.2
Cardiovascular (PAR*)	< 10.0	10.1-15.0	15.1-20.0	20.1-30.0	>30.0
Hematologic (platelet count –x 10 ⁻³)	>120	81-120	51-80	21-50	< 20
Neurologic (Glasgow coma score)	15	13-14	10-12	7-9	< 6

The GOSE is defined as:

- 1. Dead
- Vegetative state
- 3. Lower severe disability
- 4. Upper severe disability

- 5. Lower moderate disability
- 6. Upper moderate disability
- 7. Lower good recovery
- 8. Upper good recovery

Procedures to assess safety:

The safety of the EPR procedures will be continually monitored during the subject's hospitalization. Although complications specifically associated with the EPR procedures will likely be difficult to differentiate from complications arising from the subject's trauma and/or standard resuscitative efforts, we will attempt to do so. These could include, but are not limited to, injuries to vascular structures, air or clot embolism, and hemolysis. Hypothermia can lead to coagulopathy.

Induction of EPR in a pulseless trauma victim bears the risk of survival with significant neurologic dysfunction after restoring circulation in a patient who would otherwise have expired. As this outcome is possible with standard care also, this will be difficult to assess, but will be monitored in relation to the concurrent control group.

Outcome data and data analysis.

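### In subjects alive to be scored, the neurologic MODS item can partly reflect sedation or blockade given with EPR-only cooling, and the case report form does not record either

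*Protocol*

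**What the plan says.** Protocol section XI (Procedures to assess efficacy) lists MODS as a secondary outcome, compared between the EPR group and the concurrent and historical controls. It says "The MODS Score (Table) will be utilized to quantify the level of organ system dysfunction", and that for both arms "the medical record will be utilized to determine the occurrence of multiple organ system dysfunction or death". The table in that section has six items, each scored 0 to 4. The row that begins "Neurologic (Glasgow coma score" gives 0 points for a score of 15, 1 for 13-14, 2 for 10-12, 3 for 7-9 and 4 for 6 or less.

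On treatment after EPR, section VII (Clinical protocol) says: "Mild hypothermia (Tty 34°C) may be maintained for 12 h to optimize neurologic recovery using external cooling plus sedation and paralysis as needed". It also says: "Shivering will be treated with sedation (propofol), analgesia (fentanyl), and, if necessary, neuromuscular blockade". Longer cooling may be considered in selected subjects whose neurologic function is poor at 12 hours. The same section names the aspects that differ from standard trauma care, among them "reperfusion/rewarming using CPB, post-resuscitation mild hypothermia, and the potential for long-term ECLS".

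Appendix B (Daily Followup) has a field for the best Glasgow coma score of the day. As shown, the form has no field for sedation or neuromuscular blockade.

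Section VII (Outcome data and data analysis) names MODS among the outcomes compared between groups. Its next paragraph makes further investigation depend partly on lack of inferiority on the secondary endpoints. The parallel paragraph in section XI has the same condition, but its list of secondary outcomes omits MODS.

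**The concern.** A coma score depends on eye opening, speech and movement. Full neuromuscular blockade abolishes all three, so a paralysed subject falls in the lowest band and takes 4 points whatever the state of the brain. Sedation alone pushes in the same direction, less predictably. The protocol supplies a reason for both drugs, the cooling, in one arm only. In that arm the item can then measure the study treatment, and the form gives an analyst no means of telling which scores are affected.

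With 10 EPR subjects and 10 concurrent controls, few of the controls expected to survive, one or two such scores could colour the MODS comparison. That comparison is one of those meant to inform the decision to proceed.

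**Working it through.** The protocol states no figure for this point, so there is none to reproduce. The check is arithmetic on the MODS table and on the cooling schedule.

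**Inputs**
- Six items of 0 to 4 points, with the coma score bands above (section XI, MODS table).
- Cooling to below 10°C, rewarming to 34°C at a target of 0.5°C/min, then an optional 12 h at 34°C (section VII, Clinical protocol).
- Daily best coma score (Appendix B).
- 10 concurrent controls (section VII). Chance of survival under standard care below 10% (sections X and XIV), and 7% in the cited review of emergency department thoracotomies (section VII, Rationale).
- Not stated in the protocol: the day or summary used for MODS, how a sedated coma score is treated, how deaths are scored, and whether controls are sedated.

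**Step 1. Weight of the item.** 6 × 4 = 24 points, and 4 / 24 = 16.7% of the range. This is a ceiling, not an expected effect.

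**Step 2. Shift on one affected day.** If the recorded score falls to 6 or less because of drugs, the extra points depend on what the score would have been:

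| Score without drugs | Item points | Points if recorded as 6 or less | Extra |
|---|---|---|---|
| 15 | 0 | 4 | 4 |
| 13-14 | 1 | 4 | 3 |
| 10-12 | 2 | 4 | 2 |
| 7-9 | 3 | 4 | 1 |
| 6 or less | 4 | 4 | 0 |

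The shift is also 0 if the best score that day was taken off sedation and blockade.

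**Step 3. How long it lasts.** Rewarming takes (34 − 10) / 0.5 = 48 min. With 12 h at 34°C that is about 13 h, plus the time for the drugs to wear off. It mainly touches the first one or two daily scores.

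**Step 4. Effect on a summary score.** Shift in a mean = extra points × affected days / days averaged. Assuming a 7-day mean and 1 to 4 extra points:
- 1 affected day: 1 × 1 / 7 = 0.14 to 4 × 1 / 7 = 0.57 points.
- 2 affected days: 1 × 2 / 7 = 0.29 to 4 × 2 / 7 = 1.14 points.

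A 14-day mean halves these. If the worst daily score were used instead, a shift of up to 4 points could remain in full.

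**Step 5. What the comparison rests on.** With control survival p, the expected number of survivors among 10 is 10p and P(none) = (1 − p)^10. The 5% value is an assumed lower figure.

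| p | Expected survivors | P(none) |
|---|---|---|
| 5% | 0.5 | 0.60 |
| 7% | 0.7 | 0.48 |
| 10% | 1.0 | 0.35 |

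Survival is only a rough stand-in for living long enough to be scored. Even so, the rule for scoring deaths could outweigh a shift of the size in Step 4.

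**The case against.** The strongest reply is that the effect is small and avoidable. Cooling is optional, sedation and paralysis are given as needed, and the nominal period is half a day. The daily field asks for the best score, so an assessment outside the drug window can remove the shift. The full 4 points require an underlying score of 15 soon after exsanguination arrest and thoracotomy. Longer cooling is reserved for subjects with poor neurologic function, whose score would be low anyway. All of this stands, and it is why the size is given as a range starting at 0.

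A second reply is that scoring rules for sedated subjects belong in a statistical analysis plan, which is not shown. That stands for the choice of rule. But a rule cannot act on a status that the form does not carry, and the form is part of this protocol.

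Three stronger readings are tempting:
- *That MODS is biased against EPR overall.* The documents do not say that control survivors are unsedated or how deaths are scored, and they put expected mortality under standard care above 90% (section XIII). The net direction is open.
- *That the drug effect can never be separated afterwards.* MODS is determined from the medical record, and section XII keeps source documents. Sedation status might be recovered by returning to the charts; what the protocol lacks is its routine capture.
- *That the row beginning "Cardiovascular (PAR" cannot be scored because the form has no field for it.* The text as shown does not define the abbreviation, and scoring is not restricted to form fields. Adding that item's 4 points to the neurologic 4 would also combine unlike things.

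**Conclusion.** The point holds in limited form. Among subjects alive to be scored, an item worth 4 of 24 points can be raised by drugs given with cooling that the protocol provides only after EPR, and the form does not mark the affected scores. The shift is 0 to 4 points on an affected day. Under the assumed 7-day mean, with 1 to 4 extra points, it is about 0.1 to 1.1 points for one or two affected days.

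This rests on some EPR subjects being sedated or paralysed when their best daily score is taken, which the protocol permits but does not require. The link to the decision to proceed is looser than it first appears: no MODS margin is given, and one of the two paragraphs stating the condition leaves MODS out of its list. This is a measurement weakness worth correcting because the correction is so cheap, not a reason to discard MODS.

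**What to change.** Add to Daily Followup in Appendix B, for both arms, a yes/no box for sedation or neuromuscular blockade at the time of the recorded coma score. Add a sentence under the MODS table saying that the between-group comparison is reported both with all six items and without the neurologic item, and that coma scores taken under sedation or blockade are flagged.

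The cost is one form field and one extra tabulation, with no new procedure and no change to care. Without the neurologic item the maximum is 20 points and the score is less comparable with published ones, so the six-item score stays alongside. Keeping both also avoids losing in-hospital neurologic dysfunction, which GOSE at discharge or at 6 and 12 months does not measure. Historical controls will not have the box completed prospectively, so for them the score without the neurologic item is the cleaner comparison.

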Appendix A: Subject Eligibility Checklist

Inclusion Criteria

Yes	No	Criterion
		Penetrating trauma with clinical suspicion of exsanguinating hemorrhage
		Age 18-65
		At least 1 sign of life at the scene (pulse, respiratory efforts, spontaneous movements, reactive pupils)
		Loss of pulse <5 min prior to ED arrival or in the ED or operating room
		ED thoracotomy performed without immediate return of a palpable pulse in the carotid arteries after clamping the descending thoracic aorta
Exclu	sion crit	eria
Subje	cts will be	e excluded for any of the following:
		No signs of life for greater than 5 min prior to the decision to initiate EPR. This time frame is defined as the time from loss of pulse to the decision to switch to EPR.
		Age is >65 years or <18
		Obvious non-survivable injury
		Suggestion of traumatic brain injury, such as significant facial or cranial distortion
		Electrical asystole
		Rapid external assessment of the injuries suggests massive tissue trauma involving multiple body regions (for example, a crushed limb, distorted chest anatomy, or pelvic instability).
		Pregnancy
		Prisoners
		Those with aortic arch injury that would preclude flush should be excluded from study Participation
		Active Military personnel

Appendix B: Case Report Form

OVERVIEW OF SUBJECT DATA

EPR ID	
DATE OF INJURY	
HOSPITAL	
AGE	
ETHNICITY	
GENDER	
MECHANISM OF INJURY	
TIME PULSE LOST	
TIME EPR DECISION	
OBVIOUS NON SURVIVABLE	
EVIDENCE OF TBI	
ASYSTOLE	
MASSIVE TRAUMA	
PREGNANCY	
PRISONER	
TRANSPORTATION TYPE	
AGENCY NAME	
VEHICLE #	
TIME 911 CALL	
TIME ARRIVAL AT SCENE	
TIME DEPARTING SCENE	
TIME ED ARRIVAL	

ED Resuscit	ation Summary	Daily	Followup
WORST SBP		WORST SBP	
WORST DBP		WORST DBP	
WORST HR		WORST HR	
WORST RR		WORST RR	
BEST GCS		BEST GCS	
CRYSTALLOIDS		CRYSTALLOIDS	
COLLOIDS		COLLOIDS	
PRBC		PRBC	
FFP		FFP	
PLATELETS		PLATELETS	
CRYO		CRYO	
НВ		НВ	
WBC		WBC	
PT		РТ	
PTT		PTT	
PLT COUNT		PLT COUNT	
PAO2		PAO2	
SAO2		SAO2	
FIO2		FIO2	
VENTILATOR RATE		VENTILATOR RATE	
VENTILATOR TV		VENTILATOR TV	
CREAT		CREAT	
BILIRUBIN		BILIRUBIN	

ED Thoracotomy EPR ID OPERATION TITLE OP DATE TIME START TIME CROSS CLAMP AORTA TIME UNCLAMP AORTA TIME AORTIC CANNULA PLACED TIME FLUSH STARTED TIME GOAL TEMP REACHED TIME FLUSH COMPLETED STERNUM TRANSECTED? **BLOOD LOSS FROM STERNUM** EBL OP CRYSTALLOIDS OP COLLOIDS OP PRBC OP UO TIME CBP STARTED TIME CBP STOPPED **OPERATIONS** EPR ID **OPERATION TITLE** EBL OP DATE OP CRYSTALLOIDS **OP COLLOIDS** OP PRBC OP UO

	INJURIES		
	EPR ID		
INJURY I	REGION		
ABBREVIATED INJURY SEVERITY			
(COMPLICATION		
EPR ID			
COMPLICATION			
INFE EPR ID INFECTION DATE OF ONSET	CTION COMPLICATIONS		
	ONG TERM FOLLOW UP		
ALIVE			
GOSE			
RESPONDENT			

MANUFACTURER INFORMATION

IRB#	Principal Investigator:
Event date:	Date event reported to PI:
Subject ID:	Protocol: Same Different
Event report: Initial Follow-up #	Enrollment site: XXXXX
Research Drug/Device/Intervention: Brief Description of Event:	
Action Taken:	
Causality: Definite Possible (there is a reasonable possibility that the adverse event, incident, experience or outcome may have been caused by the procedures involved	Event Severity: Serious (meets one of the following criteria) A modification should be considered. >Death >Life threatening (places subject at immediate risk
in the research) Unrelated	of death from the event as it occurred) >Results in inpatient hospitalization or prolongation of existing hospitalization >Results in a persistent or significant
Probability: Expected	disability/incapacity >Results in a congenital anomaly/birth defect >Based upon appropriate medical judgment, may
